15.2 TREATMENT FAILURES

The following situations will be considered treatment failures and participants will be withdrawn from the trial:

- 30% increase in HDRS-17 score compared to baseline.
- Suicidal attempts / completion
- Device related SAE
- 15.3 LOST TO FOLLOW-UP (LTFU)

Participants who miss the final, 10-week study visit will be regarded as Lost to Follow-Up. As described in the Statistical Analysis Plan, these subjects will be included in the primary analysis through Multiple Imputation. Therefore, this definition of LTF only applies to study operations and not data analysis. Curebase or site staff should perform and document a minimum of three attempts to contact them via phone to complete the final study visit prior to considering the participant LTFU. The Curebase or site staff should document the date and type of attempted communication.

All efforts should be made to have participants complete all follow-up visits.

15.4 WITHDRAWALS

Participants have the right to withdraw from the clinical investigation at any time and for any reason. The Principal Investigator will ask the reason for their withdrawal and will record all information regarding the participant discontinuation.

A Participant may be withdrawn from the clinical investigation for the following reasons:

- Participants may choose to withdraw from the clinical investigation under the terms of the Declaration of Helsinki and their consent documentation without having to give a reason;
- Any unanticipated adverse event which, in the opinion of the Principal Investigator, is related to the treatment and will endanger the well-being of the participant if treatment is continued;
- Development of any intercurrent illness(es), infection or condition(s) that might interfere with the clinical investigation;
- Non-compliance with the clinical investigation procedures deemed by the Principal Investigator to be sufficient to cause discontinuation;
- Any problem deemed by the Investigator to be sufficient to cause discontinuation.

Participants will be withdrawn from the trial if they do not comply with the intervention, namely if they are unable to have a minimum of 60% of the tDCS session (22 (660 minutes) out of 36 sessions at week 10) during the blinded phase, or if they develop serious adverse effects from any part of the study. Recording of the reasons for withdrawal will be made. Their GP will be informed about their withdrawal, and they will have a telephone follow up at 1 month following their withdrawal.

If a participant is withdrawn, their device is disabled to make sure they cannot continue the treatment.

Regardless of the reason for withdrawal, data available for the participant at the time of withdrawal, including the reason for withdrawal, will be entered on the Case Report Forms. The research staff will request to have an optional early termination visit to collect the same data as at the week 10 and week 20 interview. The Principal Investigator will treat all participants discontinued from the investigation due to an unanticipated adverse event, directly related to the investigation, until the reaction resolves. A participant that has been withdrawn from the study after treatment start will not be replaced.

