15 EARLY DISCONTINUATION: PARTICIPANTS

15.1 TECHNICAL FAILURES

In case the Flow device or the participant's smartphone breaks, and it cannot be replaced within 10 days, and the participant has not already completed 22 sessions, this will be considered a technical failure, and the participant will be withdrawn from the trial.

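### Sections 15.1, 15.2, 15.4 and 15.5 end trial participation where stopping stimulation would do, and nothing keeps these participants in HDRS-17 visits to Week 10

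*Protocol*

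**What the plan says.** Four sections of the protocol end a participant's time in the trial by rule.

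- Section 15.1 covers a broken device or phone: if it breaks "and it cannot be replaced within 10 days, and the participant has not already completed 22 sessions", then "this will be considered a technical failure, and the participant will be withdrawn from the trial".
- Section 15.2 lists a 30% HDRS-17 rise over baseline, a suicide attempt or completion, and a device-related SAE: "The following situations will be considered treatment failures and participants will be withdrawn from the trial".
- Section 15.4 covers too few sessions: "Participants will be withdrawn from the trial if they do not comply with the intervention, namely if they are unable to have a minimum". The minimum is set at 60% of sessions, spelled out as "22 (660 minutes) out of 36 sessions at week 10". It adds serious adverse effects from any part of the study.
- Section 15.5 withdraws participants who become pregnant.

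Section 15.4 then says: "If a participant is withdrawn, their device is disabled to make sure they cannot continue the treatment". On assessment it says: "The research staff will request to have an optional early termination visit to collect the same data as at the week 10" and Week 20 interviews. The early termination column of Table 1 includes HDRS-17, and footnote 8 makes the visit depend on the participant's agreement. For participants withdrawn under the session or serious-adverse-effect rule, section 15.4 also provides a telephone call one month later, with no HDRS-17 named.

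Section 15.3, on loss to follow-up, states: "All efforts should be made to have participants complete all follow-up visits". It also requires at least three contact attempts before a missed Week 10 visit counts as lost. Section 15.6 provides for using data already collected from those who leave. Section 22.5 lists withdrawal as an alternative to completing the Week 10 visit when it sets the time of analysis. Section 22.3.3 puts every randomised participant with at least one treatment into the mITT set, apart from those randomised in error, and section 22.5 uses that set for the primary endpoint.

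**The concern.** Stopping stimulation and leaving the trial are different events, and these sections treat them as one. The primary analysis keeps the participant, while the protocol's own rules end that participant's scheduled measurement. A mixed model or multiple imputation can keep such a person in the analysis, but it cannot supply a Week 10 score that was not taken.

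The rules differ in what they put at risk. Withdrawal for too few sessions matters most, because low adherence may go with a different later course. After a 30% HDRS-17 rise the triggering score is already on file, so the loss is mainly of precision. Device failure has no evident link to outcome. To the extent that Week 10 scores are missing for adherence reasons, the primary result depends on how the model assumes those participants fared.

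**Working it through.** **1. The plan's own figures.** Inputs from section 22.2: difference 3.2; SDs 7.1 and 7.9; one-sided alpha 0.025; 1:1 allocation. Common SD = sqrt((7.1² + 7.9²)/2) = 7.51. A two-sample t-test (noncentral t) gives 88 per arm, or 176, for 80% power, and 87.6% power at 216. Then 216/0.80 = 270. All three stated figures reproduce, so the sample size contains no arithmetic error.

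**2. When 22 sessions become unreachable.** Section 9.2.3 and Table 2 cap sessions at 5 a week for three weeks, then 3 a week. The cumulative maximum is 5, 10, 15, 18, 21, 24, 27, 30, 33, 36. Sessions still possible after Weeks 4 to 10 are 18, 15, 12, 9, 6, 3, 0. The target is lost at the first week-end where sessions done + sessions remaining < 22.

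| Sessions done when stopping | Best total still possible | Exit (end of week) | Weeks before Week 10 | HDRS-17 visits not reached |
|---|---|---|---|---|
| 1–3 | 3 + 18 = 21 | 4 | 6 | 7 and 10 |
| 4–6 | 6 + 15 = 21 | 5 | 5 | 7 and 10 |
| 7–9 | 9 + 12 = 21 | 6 | 4 | 7 and 10 |
| 10–12 | 12 + 9 = 21 | 7 | 3 | 10 |
| 13–15 | 15 + 6 = 21 | 8 | 2 | 10 |
| 16–18 | 18 + 3 = 21 | 9 | 1 | 10 |
| 19–21 | 21 + 0 = 21 | 10 | 0 | none |

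The second column uses the top of each range. The table holds if the rule acts as soon as 22 is out of reach. If sessions are counted only at Week 10, the visit can still take place and little is lost.

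**3. What is observed before exit on the early-acting reading.** Someone who does 3 sessions in Week 1 and stops leaves at the end of Week 4, so the Week 4 HDRS-17 is taken about three weeks off stimulation. Someone who completes 15 sessions by Week 3 and stops leaves at the end of Week 8, so the Week 4 and Week 7 scores are both off stimulation. The period after stopping is often partly observed; its later part is not.

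**4. Bias, as illustration only.** The protocol gives no rate of rule-based withdrawal and no outcome after stopping, so every p and d here is assumed. Let p be the share withdrawn in an arm and d the later worsening the model does not capture. Reported minus as-randomised effect = pA × dA − pS × dS.

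- Equal p and d in both arms: 0.
- Only active participants stop, 5% to 20%, each losing the full 3.2: 0.05 × 3.2 = 0.16 to 0.20 × 3.2 = 0.64 points. This is an upper end, because step 3 shows that some of the loss would usually be seen.
- 5% active and 10% sham, d = 3.2 in both: (0.05 − 0.10) × 3.2 = −0.16.

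**5. Effect and power if scores are collected after stopping.** In the active-only illustration the effect becomes 3.2 × 0.95 = 3.04 or 3.2 × 0.80 = 2.56. The same t-test gives:

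| Effect | 216 observed at Week 10 | All 270 observed |
|---|---|---|
| 3.04 | 84.2% | 91.2% |
| 2.56 | 70.3% | 79.7% |

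The planned figure is 87.6%.

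**The case against.** The strongest reply is that the data loss is smaller than the wording of the rules suggests. The early termination visit collects HDRS-17 and is requested whatever the reason for withdrawal. Section 15.3 asks for all efforts to complete visits and requires three contact attempts. Scores taken off stimulation often exist before exit. Section 15.4 itself ties the session count to Week 10. The 20% attrition allowance may already cover these participants. Model details and sensitivity analyses belong to the SAP.

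Much of this stands. Precision is not the main issue, and a mixed model will have real information on many of these participants. Three things remain. The early termination visit is optional and not timed at Week 10. The efforts and contact attempts sit under loss to follow-up and do not say that a participant withdrawn by rule continues the schedule. And no SAP method can recover a score that the protocol does not arrange to collect.

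A reader might infer that the primary result is biased in favour of the device. The documents do not support that: the illustrated difference can be zero or take either sign, and all its inputs are assumed. Nor do they show that low session counts will be the commonest reason for withdrawal, since no rates by reason are given.

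**Conclusion.** The point holds as a modest defect that is cheap to remove. The protocol merges stopping stimulation with leaving the trial, and no passage keeps participants withdrawn by rule in the HDRS-17 schedule to Week 10, although the mITT analysis includes them once treated. On the early-acting reading of the 22-session rule, Week 10 is missed by those with 18 or fewer sessions, and Week 7 as well by those stopping after 1 to 9. On the Week 10 reading little is missed. The text supports both: being unable to reach a minimum, and disabling the device, suggest early action, while the count is expressed at Week 10.

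The timing rests on the protocol's session caps and is firm at week-end resolution. The bias and after-fix figures rest on assumed shares of 5% to 20% and an assumed full loss of effect; they show scale and are not estimates. Demonstrated bias in the primary result would be too strong a conclusion.

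**What to change.** - In sections 15.1, 15.2, 15.4 (both the session rule and the serious-adverse-effect rule) and 15.5, replace withdrawal from the trial or study with stopping stimulation. The device is disabled as now.
- Continue HDRS-17 at the already scheduled video calls through Week 10 for every randomised participant who has not withdrawn consent.
- Amend section 15.6 so that scores taken after stimulation stops are collected and used in the mITT analysis, and section 22.5 so that stopping stimulation does not count as withdrawal.
- State that the 22-session count does not end follow-up, whenever it is made.

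Which clinical events stop stimulation stays with the sponsor and investigators.

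The cost is amendment wording plus remote calls that are already in the schedule. They remain voluntary, so some Week 10 scores will still be missing. The estimate moves towards the effect regardless of stopping, which may be smaller. The sponsor should accept that choice knowingly and weigh the power figures at 216 observed as well as at 270.

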15.5 DOCUMENTATION OF EARLY DISCONTINUATION AND PREGNANCY

In every instance where a participant does not complete the study, the Investigator will document the primary reason for discontinuation in the participant's records.

All participants are free to withdraw from participation at any time, for any reason, specified or unspecified, and without prejudice. However, if a participant expresses a desire to withdraw their consent for the study, the site should attempt to obtain written documentation for their study records.

For participants that are discontinued by the Investigator, the Investigator must notify them of their discontinuation from the study in writing.

To ensure the safety of participants who become pregnant during the study, pregnant participants will be withdrawn from the study.

15.6 Use of Data from Early Discontinuation Cases

Study data collected previously for participants who withdraw from the study, are discontinued from the study by the Investigator or LTFU will be included in the data analysis and clinical study report.

15.7 ONGOING TREATMENT FOR EARLY DISCONTINUATION CASES

Participants who withdraw voluntarily or are discontinued by the Investigator will remain eligible for SOC treatment by the Investigator and study staff.

16 EARLY DISCONTINUATION: STUDY

16.1 PROCEDURE FOR SUSPENSION OR EARLY TERMINATION

The Sponsor may suspend or prematurely terminate this clinical investigation either at an individual investigational site or at all sites. A Principal Investigator, IRB/EC, or regulatory authority may suspend or prematurely terminate participation in this clinical investigation at the investigational sites for which they are responsible.

If suspicion of an unacceptable risk to participants arises during the clinical investigation, or when so instructed by the IRB/EC or regulatory authorities, the Sponsor will suspend the clinical

CONFIDENTIAL Page **47** of **69**

investigation while the risk is assessed. If an unacceptable risk is confirmed, the Sponsor will terminate the clinical investigation.

The Sponsor will consider terminating or suspending the participation of a particular investigational site or Investigator if monitoring or auditing identifies serious or repeated deviations on the part of an Investigator.

If suspension or premature termination occurs, the terminating party will justify its decision in writing and promptly inform the other parties with whom they are in direct communication.

If suspension or premature termination occurs:

The Sponsor will remain responsible for providing resources to fulfill the obligations from this protocol and existing agreements for following the participants enrolled in the clinical investigation, and the site's Principal Investigator or authorized designee will promptly inform the enrolled participants at his/her investigational site

If the study is terminated, Flow Neuroscience AB must comply with all applicable government regulations and the protocol-required participant follow-up. If discontinuation of the study should occur, the Principal Investigator must return all clinical investigation materials (including devices) to the Sponsor and provide a written statement to the IRB/EC explaining the reasons for the premature termination. All applicable clinical investigation documents shall be participant to the same retention policies, as detailed in Section 24.3.

16.2 PROCEDURE FOR RESUMING THE CLINICAL INVESTIGATION AFTER TEMPORARY SUSPENSION

When the Sponsor concludes an analysis of the reason(s) for the suspension, implements the necessary corrective actions, and decides to lift the temporary suspension, the Sponsor will inform the relevant parties of the rationale and provide them with the relevant data supporting this decision. Concurrence will be obtained from the IRB/ECs and, where appropriate, regulatory authorities before the clinical investigation resumes. If participants have been informed of the suspension, the Principal Investigator or authorized designee will inform them of the reasons for resumption.

16.3 ROUTINE CLOSE-OUT

Routine close-out activities will be conducted to ensure that the Principal Investigator's records are complete, all documents needed for the Sponsor's files are retrieved, remaining clinical investigation materials are destroyed, previously identified issues have been resolved, and all parties are notified.

17 PROTOCOL DEVIATIONS

Conformance to the protocol is essential to the quality and integrity of the clinical study. Every effort should be made to avoid any deviation from the clinical protocol. A protocol deviation is an event

whereby the clinical investigator or site personnel did not conduct the study according to the protocol.

Under emergency circumstances, deviations from the protocol to protect the rights, safety and well-being of human subjects may proceed without prior approval of the sponsor and the IRB/EC. Such deviations shall be documented and reported to the sponsor in the EDC within 5 days of knowledge. The IRB/EC should be notified of the deviation as required by IRB/EC reporting guidance.

18 CONCOMITANT MEDICATIONS/THERAPIES

For the purposes of this clinical study, only medications taken or administered for the following will be recorded *(Ensure medications reflected in incl/excl are listed here)*:

- Muscle relaxation;
- Other medications related to or given for the participant's MDD.

19 Adverse Event & Device Deficiency Reporting

Subjects will be carefully monitored during the study for possible adverse events (AEs) from the time they sign the Informed Consent Form to the time of study completion. All medical events and conditions prior to this time point are to be captured as medical history.

Any observed unanticipated AE will be fully investigated by the Investigator and classified in line with the definitions of ISO 14155:2020 below. The frequency and severity of anticipated AEs will instead be captured using the tDCS Adverse Events Questionnaire (AEQ).

All unanticipated adverse events that occur during this study will be recorded on the adverse event eCRFs and must include the following information at minimum:

- Event Description
- Date of Onset
- Date of Resolution
- Severity
- Seriousness
- Relationship to Study Device/Procedure
- Outcome

Adverse events will be reported and classified by the Investigator using the specific signs, symptoms or abnormal laboratory values, or medical diagnosis if no signs, symptoms, or abnormal laboratory values can be identified.

Significant new information and updates should continue to be captured in the subject's records and in the EDC as they become available and the adverse event should be followed until it is resolved or no further improvement is expected, or the subject is lost to follow-up.

Adverse events that meet the definitions of seriousness in Section 19.1 below should also be reported to the Sponsor per the instructions provided in Section 19.2.4 below.

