12.3 EXCLUSION CRITERIA

Participants who meet any of the following criteria will be excluded from participating in this study:

- 1. Are in a current state of mania, as determined by the YMRS or psychosis, as determined by the MINI.
- 2. Are diagnosed with vitamin or hormonal deficiencies that may mimic mood disorders, as determined by the investigator.
- 3. Are currently receiving any other interventional therapy for MDD other than a stable regimen of antidepressants or psychotherapy as defined in the inclusion criteria.
- 4. Considered to have treatment resistant depression as defined by inadequate clinical response to 2 or more trials of antidepressants at an adequate dose and duration.
- 5. Have a history of electroconvulsive therapy (ECT), transcranial magnetic stimulation (TMS), cranial electrotherapy stimulation (CES), transcranial direct current stimulation (tDCS), deep brain stimulation (DBS), or other brain stimulation.
- 6. Patient answers Yes to Questions 4, 5 or 6 on the Columbia Suicide Severity Rating Scale (C-SSRS) Triage and Risk Identification Screener.
- 7. Any previous hospitilization for suicidal behavior.
- 8. Have chronic severe insomnia (< 4 hours of sleep each night), or depression secondary to chronic insomnia or sleep apnea
- 9. Have any structural lesion (e.g., any structural neurological condition, or more subcortical lesions than would be expected for age or have had a stroke that affects stimulated area or connected areas) or any other clinically significant abnormality that might affect safety, study participation, or confound interpretation of study results, as determined by the investigator.
- 10. Have any implant in the brain (e.g., DBS) or neurocranium, or any other active implantable medical device.
- 11. Have any neurocranial defect.
- 12. Have a history of epilepsy or seizures (including history of withdrawal / provoked seizures).
- 13. Have shrapnel or any ferromagnetic material in the head.
- 14. Have any disorder that would impair the ability to complete the study questionnaires.
- 15. Have been diagnosed with autism spectrum disorder.
- 16. Are actively abusing substances (<1 week prior to enrollment).
- 17. Have a cognitive impairment (including dementia).
- 18. Have a history of mania or psychosis.
- 19. Are currently using any medications that affect cortical excitability (e.g., benzodiazepines, epileptics, etc.).
- 20. Are currently experiencing symptoms of withdrawal from alcohol or benzodiazepines.

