- 21. Have been diagnosed with Parkinsonism or other movement disorder as determined by the investigator to interfere with treatment.
- 22. Have ever taken esketamine / ketamine for treatment of depression.
- 23. Have ever been admitted to hospital for depression.
- 24. Have ever been diagnosed with obsessive-compulsive disorder (OCD) or bipolar type 1 or 2 disorder.
- 25. Is diagnosed with an active primary anxiety disorder, or PTSD, agoraphobia, anorexia or bulimia, panic or personality disorder with active symptoms.
- 26. Have a history of psychosurgery for depression.
- 27. Have any history of myocardial infarction, coronary artery bypass graft (CABG), coronary heart failure (CHF), or history of other cardiac issues.
- 28. Are currently experiencing or have a history of intractable migraines.
- 29. Are a chronic tobacco smoker, as defined by smoking by smoking >100 cigarettes (including hand-rolled cigarettes, cigars, cigarillos, etc.) in their life-time and have smoked every day for the last 7 days.

- 30. If female and of child-bearing potential, currently pregnant or breastfeeding or planning to become pregnant or breastfeed any time during the study.
- 31. Are currently a prisoner.
- 32. Are participating concurrently in another clinical investigation or have participated in a clinical investigation within the last 90 days or intend to Participate in another clinical investigation during the study, and where the participation in the other investigation might interfere with the results of this trial as deemed by the PI.
- 33. Have any medical condition or other circumstances, in the judgment of the investigator, that might interfere with the ability to complete follow-up visits and the self-reported MADRS-s in the app.
- 34. Have any condition which, in the judgment of the Investigator, would preclude adequate evaluation of the device's safety and performance.
- 35. A Subject who meets any of the exclusion criteria during study participation will be discontinued from the study

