22.3.4 PER PROTOCOL ANALYSIS SET (PP)

The Per Protocol (PP) analysis set will be comprised of the following:

- Subjects in the mITT analysis set
- Subjects with device failure within the 10-week follow-up period
- Subjects with deviation from the clinical investigation plan is caused by the investigational device or by problems with respect to tolerability

Subjects who will be excluded from the PP analysis set are as follows:

- Subjects with major protocol violations that would be expected to confound clinical assessment during follow-up as determined by the PIs.
- Subjects who took new pharmaceutical substances or treatments during the clinical investigation which are listed as an exclusion criteria;
- Subjects who do not meet the inclusion criteria or exclusion criteria.
- Users who have performed less than 10 sessions (300 minutes) during the first 3 weeks will be excluded from the analysis.

Subjects in the PP population will be analyzed in the group to which they were randomized.

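### Section 18 does not require systematic recording of excluded drugs started for reasons other than depression or muscle relaxation, although the per-protocol set and the discontinuation rule depend on them

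*Protocol*

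**What the plan says.** Protocol section 18 limits concomitant medication recording by purpose of use: "only medications taken or administered for the following will be recorded". Two purposes follow. The first is "Muscle relaxation" and the second is "Other medications related to or given for the participant's MDD". Between the rule and the list stands an instruction to the author: "Ensure medications reflected in incl/excl are listed here".

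Three other places bear on the same drugs:

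- Exclusion 19 (section 12.3) applies to people who "Are currently using any medications that affect cortical excitability (e.g., benzodiazepines, epileptics, etc". The class is defined by what the drug does, and no indication is named.
- Exclusion 35 (section 12.3) carries the exclusions into follow-up: "A Subject who meets any of the exclusion criteria during study participation will be discontinued from the study".
- Section 22.3.4 removes from the per-protocol set "Subjects who took new pharmaceutical substances or treatments during the clinical investigation which are listed as an exclusion criteria".

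Section 19.2.2 also asks that concomitant medication be weighed when the cause of an unanticipated adverse event is assessed. The schedule of procedures (section 7) and the visit descriptions (section 13) place a medication review at each visit, without saying that it covers more than section 18 lists.

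**The concern.** Section 18 decides by the reason for taking a drug. Exclusion 19 decides by the drug's effect. Where the two differ, a participant can meet an exclusion criterion during the study while the drug stays outside the recorded data.

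Three things are at stake. First, the per-protocol set could keep people whom its definition removes, and which of them are caught would depend on chance remarks at visits. Second, exclusion 35 could be applied to some participants and not to others in the same position. This matters because section 15.4 disables the device of anyone withdrawn. Third, new use of such drugs could not be tabulated by arm. Section 14 says that HDRS-17 probes insomnia, agitation and anxiety, so a reader of the trial report would reasonably want that table.

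**Working it through.** The point involves no arithmetic, and the protocol gives no figure to reproduce. The check sets the recording rule beside the eligibility criteria that concern drugs and asks, for each kind of use, whether section 18 captures it.

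| Use started during the study | Criterion concerned | Captured by section 18? |
|---|---|---|
| Change of antidepressant for depression | Inclusion 4 | Yes, depression item |
| Ketamine or esketamine for depression | Exclusion 22 | Yes, depression item |
| Benzodiazepine as a muscle relaxant | Exclusion 19 | Yes, muscle relaxation item |
| Benzodiazepine for sleep or anxiety judged part of the depression | Exclusion 19 | Arguably, because the second item also covers drugs merely related to the depression |
| Benzodiazepine for a reason unrelated to the depression | Exclusion 19 | No |
| Antiepileptic for pain | Exclusion 19 | No |

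The last two rows are a clear gap. The fourth row is left to each site's judgement, and different staff may settle it differently.

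Next, whether any other section closes the gap:

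1. The medication review at each visit (sections 7 and 13) gives no scope of its own, so section 18 governs what is written down.
2. Section 17 defines a deviation as a failure by the investigator or site staff to follow the protocol. A prescription from the participant's own doctor does not clearly fit. Inclusion 9 keeps participants under the care of a psychiatrist or primary care physician, and section 13.6 makes all study visits remote, so outside prescriptions are to be expected.
3. Inclusion 9 obliges participants to report a change of mental health provider. It does not mention new drugs.
4. Inclusion 10 lets study staff speak with healthcare providers, but no section requires them to ask about new prescriptions.

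Finally, which analyses are touched. Section 22.5 assigns the primary endpoint to mITT, section 22.9 assigns the exploratory endpoints to mITT, and sections 22.3.2 and 22.14 assign safety to the As Treated set. Section 22.3.3 restricts mITT exclusions to what was known or knowable before the first treatment, so a drug started later cannot change that set. As Treated membership depends on receiving a treatment. Only the per-protocol set uses new drug use as a criterion.

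An analysis plan cannot repair this, because membership cannot be derived from data that the protocol says are not recorded.

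**The case against.** The strongest reply is that an unrecorded drug is not an invisible one. Medication is discussed at every visit. Discontinuation under exclusion 35 is an investigator's action and does not wait for an entry in a medication log. The main reason for each discontinuation is documented (section 15.5), deviations have a signed form (section 24.1) and are adjudicated by the Clinical Events Committee (section 19.4), and monitors check that non-compliance is documented (section 21.2). Section 22.3.4 also removes major protocol violations, which is a second route out of the per-protocol set. Further, the depression item is worded broadly enough to take in many sedatives prescribed for sleep or anxiety in this population.

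Much of this stands. A reader might infer that newly started excluded drugs cannot be seen at all, or that no data exist to apply either rule. The documents do not support that: some uses are recorded outright and others may come to light. A reader might also infer that ketamine and esketamine are missed. They are not, because exclusion 22 reads "Have ever taken esketamine / ketamine for treatment of depression", and use for depression is already within the second item.

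What the reply does not supply is systematic recording. Each route it names depends on someone noticing the drug and choosing to document it. The leftover instruction shows that section 18 was meant to list the eligibility drugs, and it does not.

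**Conclusion.** The point holds in a limited form. Section 18 contradicts the rules that depend on it for one group: exclusion 19 drugs started for reasons unrelated to depression or muscle relaxation. For that group, per-protocol membership could not be derived reliably or equally in both arms, exclusion 35 could be applied unevenly, and use by arm and its part in adverse event causality could not be described from the recorded data.

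No numerical size is claimed. The protocol gives no rate of new use, and its exclusions for chronic severe insomnia, seizures, active primary anxiety or panic disorder and intractable migraine probably make such use less common.

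A reader might infer that the primary result is compromised. The documents do not support that: mITT membership is unaffected, and so is the As Treated set used for safety. The protocol defines the per-protocol set but assigns no endpoint to it. Nor does it state that these drugs change the response to stimulation; that is only an inference from exclusion 19. The conclusion assumes that sites follow section 18 as written and that no wider recording instruction exists elsewhere.

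**What to change.** Reconcile section 18 with exclusions 19 and 35 and with section 22.3.4. Record every drug class named in the eligibility criteria, including drugs affecting cortical excitability, whatever the indication, with start and stop dates. The dates are needed because the per-protocol rule turns on new use. Delete the drafting instruction. No separate item for ketamine or esketamine is needed. The change concerns data capture only and leaves the clinical rules as they are.

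The cost is slightly more data entry at medication reviews already scheduled at each visit. The change is best made while participants are still being followed, since drug use not recorded at the time may not be recoverable later.
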